## 2.2 Analysis sets

## 2.2.1 Full Analysis Set

The Full Analysis Set (FAS) includes all patients who received at least one dose of study treatment defined as either ribociclib, or letrozole, or goserelin, or leuprolide in the Core Phase.

## 2.2.2 Per Protocol Set

Not applicable.

## 2.2.3 Safety Set in Core Phase

For this study, the definition of FAS is the same as that of Safety Set in the Core Phase.

Novartis	Confidential	Page 18
SAP	22-Feb-2022 (1:27)	CLEE011A2404

#### 2.2.4 Safety Set in Extension Phase

The Safety set in the Extension Phase includes all patients who received at least one dose of study medication defined as ribociclib, or letrozole, or goserelin, or leuprolide in the Extension Phase

## 2.2.5 Other

The patient-reported outcomes (PRO) will be collected in subgroup of patients in selected countries. The PRO Analysis Set consists of all female patients in the FAS population for whom baseline and at least one post baseline PRO measurements are available.

## Patient Classification:

Patients may be excluded from the analysis populations defined above based on the protocol deviations entered in the database and/or on specific patient classification rules defined in Table 2-2.

ontonia		
Analysis set	Protocol deviations leading to exclusion	Non protocol deviation leading to exclusion
FAS	No written informed consent	No dose of study medication for Core Phase
Safety set in Core Phase	No written informed consent	No dose of study medication for Core Phase
PRO Analysis Set	No written informed consent	No dose of study medication or no post baseline PRO measurements for Core Phase
Safety set in Extension Phase	No written informed consent	No dose of study medication for Extension Phase

Table 2-2	Patient classification based on protocol deviations and non-PD
	criteria

#### Withdrawal of Informed Consent

Any data collected in the clinical database after a patient withdraws informed consent from all further participation in the trial, will not be included in the analysis. The date on which a patient withdraws full consent is recorded in the eCRF.

#### 2.2.6 Subgroup of interest

The following subgroups of interest may be used at interim and/or final analysis:

- Region (Latin American, Region Europe, Asia)
- Country (countries with at least 100 patients including, but not limited to US, Canada, Italy, Spain, France, Belgium, Czech Republic)
- Prior treatments for advanced disease (no treatments vs. chemotherapy)

Novartis	Confidential	Page 19
SAP	22-Feb-2022 (1:27)	CLEE011A2404

- Prior treatments for (neo)adjuvant (no treatments, endocrine only, chemotherapy only, both endocrine and chemotherapy )
- ECOG PS (PS 0-1 and 2)
- Liver involvement (yes vs. no)
- Lung involvement (yes vs. no)
- Lung or liver involvement (yes vs. no)
- Bone lesion only metastasis
- Other visceral/soft tissue involvement (adrenal, kidney, lymphonodes/soft tissue, etc.)
- Number of metastatic sites  $(0, 1, 2, \ge 3)$
- Age (<65, 65-<70, 70-<75, ≥75 years)
- Gender (male and female)
- Race (Asian vs. Non-Asian)
- Hormonal status at baseline (premenopausal vs. postmenopausal)

The objectives for carrying out analyses on these subgroups are to describe/characterize the treatment effect in these subgroups, to identify potential safety issues that may be limited to a subgroup of patients, or safety issues that are more commonly observed in a subgroup of patients.

With exception of male, summary tables will only be performed if at least 100 patients are present in each subgroup.

# 2.3 Patient disposition, demographics and other baseline characteristics

The Full Analysis Set (FAS) will be used for all baseline and demographic summaries and listings unless otherwise specified.

## 2.3.1 Basic demographic and background data

All demographic and baseline disease characteristics data will be summarized and listed. Categorical data (e.g. gender, race, ECOG performance status, etc.) will be summarized by frequency counts and percentages; the number and percentage of patients with missing data will be provided. Continuous data (e.g. age, body weight, etc.) will be summarized by descriptive statistics (N, mean, median, standard deviation, minimum and maximum). Body Mass Index (BMI (kg/m^2) = weight (kg) / [height (m)]) will be calculated based on weight and height at screening.

## 2.3.2 Diagnosis and extent of cancer

Summary statistics will be tabulated for diagnosis and extent of cancer. This analysis will include the following: primary site of cancer, histological grade, stage at initial diagnosis,

Novartis	Confidential	Page 20
SAP	22-Feb-2022 (1:27)	CLEE011A2404

stage at time of study entry, time since initial diagnosis, time from initial diagnosis to first recurrence/progression (in months), presence/absence of target and non-target lesions, HER2/Estrogen/Progesterone receptor status, number and type of metastatic sites involved.

The numbers and percentages of patients in the category defined by presence/absence of target and non-target lesions will be based on the data collected on RECIST target/non-target lesion assessment eCRF pages. Metastatic sites will be based on diagnosis page.

Time since initial diagnosis and Disease-free-interval will be summarized in months. This data will also be categorized into time intervals. Frequency counts and percentages will be presented for the number of patients in each interval.

## 2.3.3 Medical history

Medical history and ongoing conditions, including cancer-related conditions and symptoms entered on eCRF will be summarized and listed. Separate summaries will be presented for ongoing and historical medical conditions. The summaries will be presented by primary system organ class (SOC), preferred term (PT). Medical history and current medical conditions will be coded using the Medical Dictionary for Regulatory Activities (MedDRA) terminology. The MedDRA version used for reporting will be specified in the CSR and as a footnote in the applicable tables/listings.

## 2.3.4 Other

All data collected at baseline will be listed.

## 2.3.5 Patient disposition

Enrollment by country and center will be summarized for all screened patients and the FAS. The number (%) of treated patients included in the FAS will be presented. The number (%) of screened and not-treated patients and the reasons for screening failure will also be displayed. The number (%) of patients in the FAS who are still on treatment, who discontinued the study phases and the reason for discontinuation will be presented overall and by treatment group.

The following summaries will be provided (with % based on the total number of FAS patients):

- Number (%) of patients who are still on-treatment (based on the 'End of Core Treatment Phase' page not completed);
- Number (%) of patients who discontinued the Core Treatment Phase (based on the 'End of Core Treatment Phase' page)
- Number (%) of patients who have entered the Extension Treatment Phase (based on the 'End of Core Treatment Phase' page)
- Primary reason for study treatment phase discontinuation (based on the 'End of Core Treatment Phase' page)

## 2.3.6 Patient disposition in Extension Phase

Patient disposition in the Extension Phase will be summarized using the Safety Set in Extension Phase. The following summaries will be provided:

Novartis	Confidential	Page 21
SAP	22-Feb-2022 (1:27)	CLEE011A2404

- Number (%) of patients who are still on-treatment (based on the 'End of Extension Treatment' page)
- Number (%) of patients who discontinued the Extension Treatment Phase (based on the 'End of Extension Treatment' page)
- Primary reason for Extension Treatment Phase discontinuation (based on the 'End of Extension Treatment' page)

## 2.3.7 **Protocol deviations**

The number (%) of patients in the FAS with any protocol deviation will be tabulated by deviation category (as specified in the study Data Handling Plan) for the FAS. All protocol deviations will be listed.

The safety set in Extension Phase will be used for summary of listing of protocol deviations in the Extension Phase.

#### 2.3.8 Analysis sets

The number (%) of patients in each analysis set (defined in Section 2.2) will be summarized.

# 2.4 Treatments (study treatment, rescue medication, concomitant therapies, compliance)

#### 2.4.1 Study treatment / compliance

Duration of exposure, actual cumulative dose, dose intensity (DI) and relative dose intensity (RDI) will be summarized, separately for each component of study treatment. The duration of exposure will also be presented for the study treatment and the adjusted duration of exposure will be summarized for the investigational drug and combination partner. Duration of exposure will be categorized into time intervals; frequency counts and percentages will be presented for the number (%) of patients in each interval. The number (%) of patients who have dose reductions or interruptions, and the reasons, will be summarized.

Patient level listings of all doses administered on treatment along with dose change reasons will be produced.

The safety set in Core Phase will be used for all summaries and listings of study treatment in the Core Phase.

The safety set in Extension Phase will be used for all summaries and listings in the Extension Phase.

## 2.4.1.1 Duration of exposure to study treatment

Duration of exposure to study treatment is considered by taking into account the duration of exposure to the investigational drug and the combination partner:

Duration of exposure to study treatment (days) = (last date of exposure to study treatment) – (date of first administration of study treatment) + 1.

Novartis	Confidential	Page 22
SAP	22-Feb-2022 (1:27)	CLEE011A2404

The last date of exposure to study treatment is the latest of the last dates of exposure to investigational drug and the combination partner.

Summary of duration of exposure of study treatment in appropriate time units will include categorical summaries (<3, 3 to <6, 6 to <9, 9 to <12, 12 to <15, 15 to <18,  $\geq$ 18 months) and continuous summaries (i.e. mean, standard deviation etc.) using appropriate units of time.

#### 2.4.1.2 Duration of exposure to investigational drug and combination partner

Duration of exposure to ribociclib (days) = (last date of exposure to ribociclib) – (date of first administration of ribociclib) + 1.

Duration of exposure to letrozole (days) = (last date of exposure to letrozole) – (date of first administration of letrozole) + 1.

Duration of exposure to goserelin (days) = (last date of exposure to goserelin) – (date of first administration of goserelin) +1.

Duration of exposure to leuprolide (days) = (last date of exposure to leuprolide) – (date of first administration of leuprolide) +1.

The last date of exposure to ribociclib is defined as the last administration of a non-zero dose of ribociclib.

The last date of exposure to letrozole is defined as the last administration of a non-zero dose of letrozole.

The last date of exposure to goserelin is defined as the last administration of a non-zero dose of goserelin + 27 days.

The last date of exposure to leuprolide is defined as the last administration of a non-zero dose of leuprolide + 27 days.

Adjusted duration of exposure (days) for ribociclib is the number of ribociclib dosing days a patient would be expected to have received per protocol, given their duration of exposure to study treatment as defined above. Since ribociclib follows a 3 weeks on , 1 week off schedule, the adjusted duration of exposure to ribociclib is the duration of exposure to study treatment minus the planned off days for ribociclib. The adjusted duration of exposure to ribociclib is therefore  $21x(\# \text{ completed } 28 \text{ day cycles}) + \min(21, \text{ duration of last incompleted cycle}).$ 

For example, if the duration of exposure to ribociclib is 66 (corresponding to two cycles and 10 days), then the adjusted duration of exposure is 21\*2+10=52. If the duration of exposure to ribociclib is 108 days (corresponding to three cycles and 24 days), then the adjusted duration of exposure is 21\*3+21=84.

Specifically, let D1 represent the duration of exposure to study treatment as defined above. Then the adjusted duration of exposure is defined as D=21\*[D1/28] + min(21, D1-28\*[D1/28]) where [x] stands for the integer part of x. In this equation [D1/28] is the number of completed cycles, and D1-28\*[D1/28] is the additional number of days in the last incomplete cycle (if any). For example, if D1=30 then [D1/28]=1, D1-28\*[D1/28]=2, and D=23. If D1=7 then D=7; if D1=22 then D=21; if D1=28 then D=21, etc.

Novartis	Confidential	Page 23
SAP	22-Feb-2022 (1:27)	CLEE011A2404

The adjusted duration of exposure for ribociclib will be used to calculate the dose intensity and relative dose intensity for ribociclib.

It should be noted that when calculating the adjusted duration of exposure for ribociclib, it is derived from the duration of exposure for study treatment, not from the duration of exposure for ribociclib.

Summary of duration of exposure of investigational drug will include categorical summaries based on <3, 3 to <6, 6 to <9, 9 to <12, 12 to <15, 15 to <18,  $\geq$ 18 months intervals and using descriptive statistics (mean, standard deviation etc).

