## Date of first administration of study treatment

The date of first administration of study treatment is derived as the first date when a nonzero dose of any component of study treatment was administered as per the Dosage Administration eCRF. (Example: if 1st dose of ribociclib is administered on 05-Jan-2015, and 1st dose of letrozole is administered on 03-Jan-2015, then the date of first administration of study

Novartis	Confidential	Page 15
SAP	22-Feb-2022 (1:27)	CLEE011A2404

treatment is on 03-Jan-2015). The date of first administration of study treatment will also be referred as *start of study treatment*.

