#### 2.4.1.3 Cumulative dose and average daily dose

Cumulative dose of a study treatment is defined as the total dose given during the study treatment exposure and will be summarized for each of the study treatment components.

The **planned cumulative dose** for a study treatment component refers to the total planned dose as per the protocol up to the last date of investigational drug administration.

The **actual cumulative dose** refers to the total actual dose administered, over the duration for which the patient is on the study treatment as documented in the Dose Administration eCRF.

For patients who did not take any drug the cumulative dose is by definition equal to zero.

For continuous dosing, the actual cumulative dose is the sum of the non-zero doses recorded over the dosing period and the planned cumulative dose is the planned starting dose summed over the same dosing period.

For intermittent dosing, the actual cumulative dose should be defined based on the days when the patient is assumed to have taken a non-zero dose during dosing periods.

Average daily dose is defined as Cumulative dose (mg) / Number of dosing days. Drug free day(s) are not counted as dosing days.

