#### 2.4.1.4 Dose intensity and relative dose intensity

Dose intensity (DI) for patients with non-zero duration of exposure is defined as follows:

For ribociclib, DI is defined as

DI (mg/day) = Actual Cumulative dose (mg) / adjusted Duration of exposure (day).

For letrozole, DI is defined as

DI (mg/day) = Actual Cumulative dose (mg) / Duration of exposure (day).

For goserelin and leuprolide, DI is defined as

DI (mg/28 days) = Actual Cumulative dose (mg) / Duration of exposure (28 days).

For patients who did not take any drug the DI is by definition equal to zero.

Planned dose intensity (PDI) is the assigned dose by unit of time planned to be given to patients as per protocol in the same dose unit and unit of time as that of the Dose Intersity. The planned dose intersity for ribociclib is 600mg/day and the planned dose intersity for letrozole is 2.5mg/day. The planned dose intensity for goserelin is 3.6 mg/28 days. The

Novartis	Confidential	Page 24
SAP	22-Feb-2022 (1:27)	CLEE011A2404

planned dose intensity for leuprolide is 7.5 mg/28 days. Goserelin and leuprolide are admistered Day 1 of each cycle.

Relative dose intensity (RDI) is defined as follows for ribociclib and letrozole:

RDI = DI (mg/day) / PDI (mg/day).

For goserelin and leuprolide, RDI is defined as

RDI = DI (mg/28days) / PDI (mg/28days).

DI and RDI will be summarized separately for each of the study treatment components, but using the duration of exposure of each of the components. In particular, while calculating DI and RDI for ribociclib, the adjusted duration of exposure for ribociclib should be used instead of the duration of exposure for ribociclib. This takes account into the 'off' days when no ribociclib is expected to be administered.

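### On the most natural reading of SAP 2.4.1.2, the ribociclib RDI denominator runs to the last goserelin/leuprolide injection plus 27 days and so counts planned ribociclib days after both oral drugs have stopped

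*SAP*

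**What the plan says.** SAP 2.1.3 defines study treatment as ribociclib, letrozole and, where applicable, goserelin or leuprolide. SAP 2.4.1.1 sets the end of exposure: "The last date of exposure to study treatment is the latest of the last dates of exposure to investigational drug and the combination partner".

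SAP 2.4.1.2 then gives an end date for each component. For ribociclib and letrozole it is the last non-zero dose. For the LHRH agonists it is later: "The last date of exposure to goserelin is defined as the last administration of a non-zero dose of goserelin + 27 days", with the same rule for leuprolide.

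The adjusted duration of ribociclib is the number of ribociclib dosing days a patient should have had, "given their duration of exposure to study treatment as defined above". The section calls the study-treatment duration D1 and repeats that, for the adjusted duration, "it is derived from the duration of exposure for study treatment, not from the duration of exposure for ribociclib". The two calendar examples start elsewhere: "if the duration of exposure to ribociclib is 66 (corresponding to two cycles and 10 days", and likewise 108 days of ribociclib exposure.

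SAP 2.4.1.4 divides the actual cumulative ribociclib dose by the adjusted duration to get DI, and divides DI by 600 mg/day to get RDI.

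**The concern.** SAP 2.4.1.4 gives the purpose of the adjusted duration: to allow for "days when no ribociclib is expected to be administered", that is, the off week. The 27-day carry-over works the other way in a patient on an LHRH agonist. A depot injection given early in the stopping cycle keeps study-treatment exposure open after the tablets have stopped, and the formula fills that stretch with on-days on which nobody expected a dose. Nothing in SAP 2.4.1.1 to 2.4.1.4 caps D1 at the last oral dose.

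The tail can only lower RDI, and only in men and premenopausal women. A postmenopausal patient with identical tablets has none. Letrozole DI uses letrozole's own duration, so an adherent patient who stops both tablets on the same day can show 100% for letrozole and much less for ribociclib. An RDI summary would then mix a calculation artefact with true under-dosing, mostly in patients who stop early. Any RDI table by sex or menopausal status would carry the same artefact.

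**Working it through.** **Formula (SAP 2.4.1.2).** Adjusted duration D = 21 × [D1/28] + min(21, D1 − 28 × [D1/28]), where [ ] is the integer part.

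**The SAP's own figures.** 66 → 21 × 2 + 10 = 52; 108 → 21 × 3 + 21 = 84; 30 → 23; 7 → 7; 22 → 21; 28 → 21. All six reproduce.

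**A 66-day adherent course with injections added.** The injections are an addition here; the SAP's example has none. They are placed on Day 1 of each cycle, as SAP 2.4.1.4 states. All drugs start on the same day.

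- Ribociclib on Days 1–21, 29–49 and 57–66: 21 + 21 + 10 = 52 days, 52 × 600 = 31,200 mg. Letrozole runs to Day 66.
- Injections on Days 1, 29 and 57. LHRH exposure ends on Day 57 + 27 = 84.
- D1 = max(66, 84) = 84, so D = 21 × 3 = 63.
- DI = 31,200/63 = 495.2 mg/day. RDI = 495.2/600 = 52/63 = 82.5%.
- Excess: 63 − 52 = 11 planned days (Days 67–77), all after both tablets stopped.
- Same tablets, no LHRH agonist: D1 = 66, D = 52, RDI = 100%.

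**General form.** With Day 1 injections and full adherence, let both oral drugs stop on day x of cycle k. For x = 1 to 20, RDI = [21(k − 1) + x]/(21k), a shortfall of (21 − x)/(21k) and so at most 20/(21k). For x = 21 to 28 there is no shortfall.

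| Last oral day | Cycle, day | Days taken / D | RDI |
|---|---|---|---|
| 10 | 1, 10 | 10/21 | 47.6% |
| 66 | 3, 10 | 52/63 | 82.5% |
| 94 | 4, 10 | 73/84 | 86.9% |
| 108 | 4, 24 | 84/84 | 100% |
| 178 | 7, 10 | 136/147 | 92.5% |
| 548 | 20, 16 | 415/420 | 98.8% |

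**No injection in the last cycle.** Stop on Day 66 with the last injection on Day 29: 29 + 27 = 56, which is before Day 66, so D1 = 66 and RDI = 52/52 = 100%.

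**Average size.** If stop days were uniform over cycle days 1–28 (an assumption; the documents give no distribution), the mean excess is (20 + 19 + … + 1)/28 = 210/28 = 7.5 planned days. Dividing by 21k gives a mean shortfall of 11.9 points in cycle 3, 6.0 in cycle 6, 3.0 in cycle 12 and 2.0 in cycle 18.

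**Other injection days.** Protocol 6.1.1 lets a patient already on an LHRH agonist keep the existing 28-day schedule, so the affected stop days can shift. Injection on cycle day 8, stop on Day 63: last injection Day 36, D1 = 63, RDI = 49/49 = 100%. Injection on cycle day 15, stop on Day 77: last injection Day 71, D1 = 98, D = 77, RDI = 63/77 = 81.8%. The 20/(21k) bound is for Day 1 injections only.

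**The case against.** **The reading.** SAP 2.4.1.1 speaks of the combination partner in the singular and does not define it, and the examples for first and last administration in SAP 2.1.3 use letrozole only. If the partner means letrozole alone, there is no tail. This is possible but weaker: SAP 2.1.3 counts the LHRH agonists in study treatment, and SAP 2.4.1.2 defines their exposure end dates under a heading that names the combination partner. If letrozole alone was meant, the text should say so.

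**The choice is deliberate.** Basing the denominator on study treatment is stated outright. Counting planned ribociclib days while letrozole continues is coherent, and so is starting at the first dose of any component ("derived as the first date when a nonzero dose of any component of study treatment was administered"), which captures a delayed ribociclib start. A reader might infer that the start date is also wrong. The documents do not support that: it is a stated choice, and a start at the first ribociclib dose would not exist for a patient in the Safety Set who never took ribociclib. Only the depot tail lacks a rationale.

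**Conflict with planned cumulative dose.** A reader might also take SAP 2.4.1.3 as a contradiction, because there the planned cumulative dose "refers to the total planned dose as per the protocol up to the last date of investigational drug administration". That quantity does not enter DI or RDI, and it differs from the denominator anyway whenever letrozole outlasts ribociclib. It does not decide the point.

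**Size.** This objection largely stands. The effect shrinks with each cycle, and Protocol 4.3 plans at least 18 months of follow-up. Most scheduled visits fall on Day 1 and imaging is recommended every 12 weeks, which is three cycles. A patient stopped at a Day 1 visit before the next injection has no tail, so the uniform average is probably too high.

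**Conclusion.** The point holds on the most natural reading of SAP 2.1.3, 2.4.1.1 and 2.4.1.2. Ribociclib RDI is understated in patients on goserelin or leuprolide who stop both oral drugs mid-cycle after that cycle's injection. The illustrative case is 82.5% in place of 100%; it assumes full adherence, a same-day start and Day 1 injections. In long courses the effect is a few points or less. The documents do not give the number of patients affected.

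A reader might infer that the trial's tolerability conclusions are biased. The documents do not support that. Protocol 10.5.3.6 assesses tolerability by dose reductions or interruptions due to an adverse event, and SAP 2.4.1.5 counts these from the dosing records, not from RDI. No primary or secondary endpoint changes, and average daily dose is unaffected. Subgroup summaries are optional under SAP 2.2.6, and no RDI table by sex or menopausal status is promised.

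The mismatch between the 66- and 108-day examples and the formula stands on either reading. For the 66-day patient with Day 1 injections, following the example gives 52 planned days; following the stated rule gives 63.

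**What to change.** In SAP 2.4.1.2, for the ribociclib adjusted duration only, end D1 at the later of the last ribociclib and last letrozole administration, without the 27 days. Keep the start at the first administration of study treatment. Keep the 27 days for goserelin and leuprolide exposure and for their own DI. In SAP 2.4.1.1, say which drugs the combination partner covers.

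Reword the 66- and 108-day examples in terms of D1. The 108-day example already fits only that reading: on an undelayed schedule Day 108 is cycle day 24, an off-day for ribociclib.

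Check: for the 66-day course, D1 = 66, D = 52 and RDI = 52/52 = 100%, with or without injections. Patients whose letrozole outlasts ribociclib still have those days counted, as the SAP intends. The cost is SAP wording and one derivation line; no new data are needed.
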